## 11.6 Records Retention

Following closure of the study, the investigator must maintain all site study records (except for those required by local regulations to be maintained elsewhere), in a safe and secure location.

The records (study/ site master file) must be maintained to allow easy and timely retrieval, when needed (e.g., for a GSK audit or regulatory inspection) and must be available for review in conjunction with assessment of the facility, supporting systems, and relevant site staff.

Where permitted by local laws/regulations or institutional policy, some or all of these records can be maintained in a format other than hard copy (e.g., microfiche, scanned, electronic); however, caution needs to be exercised before such action is taken.

The investigator must ensure that all reproductions are legible and are a true and accurate copy of the original and meet accessibility and retrieval standards, including re-generating a hard copy, if required. Furthermore, the investigator must ensure there is an acceptable back-up of these reproductions and that an acceptable quality control process exists for making these reproductions.

The investigator must assure that the subject's anonymity will be maintained. On CRFs or other documents submitted to GSK CH, subjects should not be identified by their names or initials, but by an identification code. The investigator should keep a separate log of subjects' codes, names and addresses. Documents not for submission to GSK CH, e.g. subjects' written consent forms, should be maintained by the investigator in strict confidence.

Records and documents, including signed ICF, pertaining to the conduct of this study must be retained by the investigator for 25 years from the issue of the final Clinical Study Report (CSR)/ equivalent summary unless local regulations or institutional policies require a longer retention period. The minimum retention time will meet the strictest standard applicable to that site for the study, as dictated by any local laws or regulations, GSK standards/procedures, and/or institutional requirements.

No study document should be destroyed without a prior written agreement between GSK CH and the investigator. The investigator must notify GSK of any changes in the archival arrangements, including, but not limited to, archival at an off-site facility or transfer of ownership of the records in the event the investigator is no longer associated with the site.

GlaxoSmithKline Consumer Healthcare Confidential Template Version Effective: 22-Jun-2017 Page 54 of 60

Final 1.0 Clinical Protocol

## 11.7 Conditions for Terminating the Study

Premature termination of this study may occur because of a regulatory authority decision, change in opinion of the IEC, or investigational product safety problems, or at the discretion of GSK CH. In addition, GSK CH retains the right to discontinue development of  $SnF_2$  dentifices at any time.

If a study is prematurely terminated, GSK CH will promptly notify the investigator. After notification, the investigator must promptly contact all participating subjects and should assure appropriate therapy/ follow-up for the subjects. As directed by GSK CH, all study materials must be collected and all CRFs completed to the greatest extent possible. Where required by the applicable regulatory requirements, GSK CH should inform the regulatory authority(ies) and the investigator should promptly inform the IEC and provide the IEC a detailed written explanation of the termination or suspension.

If the IEC terminates or suspends its approval/favorable opinion of a trial, the investigator should promptly notify the GSK CH and provide GSK CH with a detailed written explanation of the termination or suspension.

Upon completion or premature discontinuation of the study, the GSK CH monitor will conduct site closure activities with the investigator or site staff, as appropriate, in accordance with applicable regulations including GCP, and GSK CH Standard Operating Procedures.

## 11.8 Definition of Study End/ End of Study

The end of the study will be the date of the Last Subject Last Visit (LSLV). For this study the LSLV will be the primary completion date (PCD).

# 13 APPENDIX

### 13.1 Appendix I – Instructions

#### INSTRUCTIONS

Brush twice a day (morning and evening) for 1 timed minute.

Each time you brush:

• Dispense a ribbon of toothpaste covering the length of the toothbrush head (see below picture).

• Set your timer for 1 minute, and then brush all the teeth in your mouth in your usual manner for 1 timed minute.

• Record each brushing in the diary. Note any changes to these brushing procedures and reasons for changes (e.g. missed brushings, extra brushings) too.

GlaxoSmithKline Consumer Healthcare Confidential

Template Version Effective: 22-Jun-2017

Page 57 of 60

• Record any changes in your smoking habits, health, medications (prescription and over the counter medications) or treatments in the diary.

- Bring your diary card (completed and not completed), toothpaste and toothbrush to the next study visit.
- Please do not remove or deface any part of the study label.

Please do not share your study toothpaste with anybody and do not discuss with the examiner your experience with your assigned toothpaste (taste, color and smell).

# 13.2 Appendix II - Abbreviations

The following is a list of abbreviations that may be used in the protocol.

Abbreviation	Term
ABL	aluminum barrier laminate
AE	adverse event
ANCOVA	analysis of covariance
CI	confidence interval
CRF	case report form
DMS	data management system
DH	dentine hypersensitivity
EAR	erosion, abrasion, recession
EDC	electronic data capture
EDP	exposure during pregnancy
FSFV	first subject first visit
FSH	follicle stimulating hormone

Table 13-1Abbreviations

GlaxoSmithKline Consumer Healthcare Confidential Template Version Effective: 22-Jun-2017 Page **58** of **60** 

	Document Name	208153 Clinical Protocol.docx		
	Туре	Version	Document Identifier	Effective Date
	eldo clinical doc	3.0; Most-Recent; Effective; CURRENT	090032d580d852b1	3-Aug-2017 05:58:20
ne	Reason For Issue	Auto Issue		0
St	Stannous fluoride			

Abbreviation	Term
GCP	Good Clinical Practice
GCS	Global Clinical Supplies
GSK CH	GlaxoSmithKline Consumer Healthcare
IB	investigator's brochure
ICH	International Conference on Harmonisation
IEC	Independent Ethics Committee
ITT	intent to treat
IUD	intrauterine device
LSLV	last subject last visit
MedDRA	medical Dictionary for Regulatory Activities
MoH	Ministry of Health
MGI	Modified Gingival Index
NaF	sodium fluoride
N/A	not applicable
OHT	oral hard tissue
OST	oral soft tissue
OTC	over-the-counter
P&G	Proctor and Gamble
PI	principal investigator
PII	personally identifiable information
РР	per protocol
РТ	preferred term
PRO	patient reported outcome
SAE	serious adverse event
SAP	statistical analysis plan
SnF 2	stannous fluoride
SnCl 2	stannous chloride
SMFP	sodium monofluorophosphate
SOC	system organ class
SOP	standard operating procedure
SUSAR	suspected unexpected serious adverse reactions
SS	safety statement

## GlaxoSmithKline Consumer Healthcare Confidential Template Version Effective: 22-Jun-2017 Page **59** of **60**

Document Name	208153 Clinical Protocol.docx		
Туре	Version	Document Identifier	Effective Date
eldo clinical doc	3.0; Most-Recent; Effective; CURRENT	090032d580d852b1	3-Aug-2017 05:58:20
Reason For Issue	Auto Issue		0

Stannous fluoride

Protocol Number 208153 Final 1.0 Clinical Protocol

Abbreviation	Term
SSRD	single reference safety document
TMF	trial master file

GlaxoSmithKline Consumer Healthcare Confidential Template Version Effective: 22-Jun-2017 Page **60** of **60** 

## Document History

Document	Version Date	Summary of Changes (New analysis or Change in planned analysis)
Final Analysis Plan	14-Dec-2017	Not applicable (N/A)

---

**Abbreviations**

Abbreviation	Definition
AE	Adverse Event
ANCOVA	Analysis Of Covariance
BDRM	Blinded Data Review Meeting
CI	Confidence Interval
DH	Dentinal Hypersensitivity
eCRF	Electronic Case Report Form
GCS	Global Clinical Supplies
GSKCH	GlaxoSmithKline Consumer Healthcare
ITT	Intent-To-Treat
MedDRA	Medical Dictionary For Regulatory
N	Number Of Subjects
NAF	Sodium Fluoride
OST	Oral Soft Tissue
PP	Per Protocol
ppm	Parts Per Million
RLR	Review Listing Requirement
SAE	Serious Adverse Event
SD	Standard Deviation
SE	Standard Error
SMFP	Sodium Monofluorophosphate
SnCl 2	Stannous Chloride
SnF 2	Stannous fluoride
SOC	System Organ Class
w/w	Weight/Weight

The purpose of this Statistical Reporting and Analysis Plan is to describe the planned analyses and outputs to be included in the Clinical Study Report for Protocol 208153.

## 1 Summary of Key Protocol Information

The purpose of this trial is to demonstrate the efficacy and safety of a experimental 0.454% weight/weight (w/w) Stannous fluoride (SnF2) dentifrice to treat the symptoms of Dental Hypersensitivity (DH). Efficacy will be demonstrated as a treatment difference in favour of the 0.454% w/w SnF2 dentifrice versus the Negative Control dentifrice for the primary efficacy outcome, Schiff sensitivity score at Week 8. Safety will be demonstrated through assessment of adverse events (AEs).

### 1.1 Study Design

#### Overall Design

This will be a single centre, randomized, controlled, examiner-blind, 3 treatment arm, parallel group design study, stratified by maximum baseline Schiff sensitivity score (of the 2 selected test teeth), with a treatment period of 8 weeks, to investigate the clinical effectiveness of an experimental SnF2 dentifrice in the reduction of DH. DH will be assessed at Baseline, and after 4 and 8 weeks treatment.

The study will be conducted in healthy subjects with pre-existing self-reported and clinically diagnosed tooth sensitivity at Screening, in a Chinese population.

An acclimatization period of 2-6 weeks will be included in this study, given that 2 weeks is understood to be an expected amount of time to minimize the potential for carry over effects from prior use of anti-sensitivity products.

In line with Chinese Ministry of Health guidelines [Ministry of Health (China), 2010] for the testing of functional dentifrices (desensitizing), a standard fluoride dentifrice with no specific anti-sensitivity, anti-gingivitis and anti-plaque activity (Chinese marketed Colgate Triple Protection) will be included as the negative control (Negative Control). A Chinese marketed positive control (Positive Control) dentifrice with sensitivity benefits (Crest 7-Effects Strengthen Dental Enamel toothpaste, containing stannous chloride (SnCl2)) will also be included in this study design as a benchmark of performance in the Chinese population.

### 1.2 Study Objectives

Objectives	Endpoints
Primary Objective	Primary Endpoint

 
To compare the clinical efficacy of an experimental 0.454% w/w SnF2 dentifrice for the relief of DH, as elicited by an evaporative air stimulus (with Schiff sensitivity score), against
 
	
 
Change from baseline in Schiff sensitivity score at 8 weeks.
 

Objectives	Endpoints
a negative control dentifrice, when used twice daily for 8 weeks.	
Secondary Objectives	Secondary Endpoints

 
To compare the clinical efficacy of an experimental 0.454% w/w SnF2 dentifrice for the relief of DH, as elicited by a tactile stimulus (Yeaple probe), against a negative control dentifrice, when used twice daily for 8 weeks.
 
	
 
Change from baseline in tactile threshold (Yeaple probe) at 8 weeks.
 

Exploratory Objectives	Exploratory Endpoints

 
To compare the clinical efficacy of an experimental 0.454% w/w SnF2 dentifrice for the relief of DH, as elicited by an evaporative air stimulus (with Schiff sensitivity score), against a positive control dentifrice, when used twice daily for 4 and 8 weeks.
 
	
 
Change from baseline in Schiff sensitivity score at 8 weeks.
 

 
To compare the clinical efficacy of an experimental 0.454% w/w SnF2 dentifrice for the relief of DH, as elicited by an evaporative air stimulus (with Schiff sensitivity score), against a negative control dentifrice, when used twice daily for 4 weeks.
 
	
 
Change from baseline in Schiff sensitivity score at 4 weeks.
 

 
To compare the clinical efficacy of an experimental 0.454% w/w SnF2 dentifrice for the relief of DH, as elicited by a tactile stimulus (Yeaple probe), against a negative control dentifrice, when used twice daily for 4 weeks.
 
	
 
Change from baseline in tactile threshold (Yeaple probe) at 4 weeks.
 


 
To compare the clinical efficacy of an experimental 0.454% w/w SnF2 dentifrice for the relief of DH, as elicited by a tactile stimulus (Yeaple probe), against a positive control dentifrice, when used twice daily for 4 and 8 weeks.
 
	
 
Change from baseline in tactile threshold (Yeaple probe) at 4 and 8 weeks.
 

 
To compare the clinical efficacy of a positive control dentifrice for the relief of DH, as elicited by a tactile
 
	
 
Change from baseline in tactile threshold (Yeaple probe) at 4 and 8 weeks.
 

Stannous Fluoride (SnF2)

208153

Final Statistical Reporting and Analysis plan V1.0 14 Dec 2017

Objectives	Endpoints
stimulus (Yeaple probe), against a negative control dentifrice, when used twice daily for 4 and 8 weeks.	

To compare the clinical efficacy of a positive control dentifrice for the relief of DH, as elicited by an evaporative air stimulus (with Schiff sensitivity score) against a negative control dentifrice, when used twice daily for 4 and 8 weeks

	

Change from baseline in Schiff sensitivity score at 4 and 8 weeks.

Safety	

To evaluate the safety and oral tolerability of the test dentifrices when used twice daily for 8 weeks.

	

Adverse Events

### 1.3 Treatment

The following study products will be supplied by Global Clinical Supplies (GCS), Glaxosmithkline Consumer Health (GSK CH):

- **Test Product:** Experimental dentifrice containing 0.454% SnF2 and 0.072% NaF (1450 ppm fluoride in total); CCI [REDACTED].
- **Negative Control:** Colgate Triple Protection dentifrice containing 1400 ppm fluoride as sodium monofluorophosphate (SMFP); Chinese Marketplace.
- **Positive Control:** Crest 7-Effects Strengthen Dental Enamel dentifrice containing SnCl2 and 0.15% NaF (1450 ppm fluoride in total); Chinese marketplace.

Other items to be supplied by the GCS Department, GSK CH:

- **Acclimatization dentifrice:** Colgate Strengthen Fresh Dentifrice containing 1400ppm fluoride as SMFP (Chinese Marketplace).
- Aquafresh Clean Control Toothbrush (UK market place).
- Countdown timers.

### 1.4 Sample Size Calculation

Change from baseline in Schiff sensitivity score will be used to evaluate treatment effects with regard to the primary objective. With 55 evaluable subjects per group, the study will have 80% power to detect a mean difference of 0.33 (standard deviation [SD]=0.619) in change from baseline in Schiff sensitivity score after 8 weeks of treatment.

The estimate of SD was obtained from GSKCH study 205794. The sample size is based on carrying out 2-tailed 2 sample t-test at a 5% significance level.

Therefore, to allow for dropouts a sufficient amount of subjects will be screened to randomize approximately 180 subjects to ensure 165 subjects (approximately 55 per arm) complete the study.

## 2 Planned Analyses

### 2.1 Interim Analysis

No interim analysis is planned.

### 2.2 Final Analyses

The final planned primary analyses will be performed after the completion of the following sequential steps:

1. All subjects have completed the study as defined in the protocol.
2. All required database cleaning activities have been completed and database has been locked.

3. All criteria for unblinding the randomization codes have been met and the randomization codes have been distributed.

### **3 Considerations for Data Analyses and Data Handling Conventions**

#### **3.1 Baseline Definition**

For all endpoints, the baseline value will be the latest Day1 (Visit 2) pre-dose assessment with a non-missing value.

Unless otherwise stated, if baseline data is missing no derivation will be performed and will be set to missing.

#### **3.2 Subgroups/Stratifications**

Subgroups are not defined for this trial.

Eligible subjects will be stratified according to their maximum baseline Schiff sensitivity score of the 2 selected teeth. The stratification factor will give rise to 2 strata.

Stratum 1: Maximum Schiff=2. These are subjects with maximum baseline Schiff sensitivity score of 2 for the 2 selected test teeth.

Stratum 2: Maximum Schiff=3. These are subjects with the maximum baseline Schiff sensitivity score of 3 for the 2 selected test teeth.

Efficacy variables will be analyzed accounting for strata.

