	Visit 1	period	Visit 2 Day 1 Baseline	Visit 3 Day 29±3	Visit 4 Day 57±3
Visual Compliance Check of Returned Study Dentifrice and Review of Subject Diary			х	х	х
Adverse Events 	Х		Х	Х	Х
Study Conclusion					Х

Abbreviations: OST = Oral Soft Tissue; OHT = Oral Hard Tissue; EAR = Erosion, Abrasion, Recession; MGI = Modified Gingival Index.

- Qualifying Schiff sensitivity and tactile threshold scores will be recorded in the case report form (CRF). Evaporative air assessment to
  follow tactile assessment; minimum 5 minutes time lapse between the two assessment types for tooth recovery. At Screening,
  maximum force for tactile = 20g.
- 2. Inclusion criteria 6d and exclusion criteria 13b.
- 3. Subject is instructed to bring all supplies back to next visit.
- 4. Study supplies to be returned to subject (for use at home) after supervised brushing.
- 5. At Baseline, maximum force = 20g., at all subsequent visits maximum force = 80g.
- 6. Evaporative air assessment to follow tactile assessment; minimum 5 minutes time lapse between the two assessment types for tooth recovery.
- Subject is instructed to bring all supplies back to subsequent visits for compliance checks. Study supplies to be returned to subject after supervised brushing. At the Week 4 visit subjects will be re-dispensed with a new diary and new tubes of their allocated dentifrice prior to conducting their supervised brushing.
- 8. Any serious adverse event assessed as related to study participation that occurs subsequent to the signing of informed consent and any adverse event that occurs subsequent to the first dose of the acclimatization dentifrice will be recorded.

GlaxoSmithKline Consumer Healthcare Confidential Template Version Effective: 22-Jun-2017 Page 9 of 60

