d) Minimum of two, non-adjacent accessible teeth (incisors, canines, pre-molars), with signs of sensitivity, measured by response to a qualifying tactile stimulus (Yeaple ≤20g) and evaporative air assessment (Schiff sensitivity score ≥2). The two selected test teeth must have also qualified at Screening for this criteria.

**Note:** The Investigator will select two *Test Teeth* from those which meet *both* the tactile threshold and Schiff sensitivity score criteria, in addition to meeting all other criteria. *Test Teeth* should not be adjacent to each other and preferably in different quadrants.

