# 10 STATISTICAL CONSIDERATIONS AND DATA ANALYSES

## 10.1 Sample Size Determination

Change from baseline in Schiff sensitivity score will be used to evaluate treatment effects with regard to the primary objective. With 55 evaluable subjects per group, the study will have 80% power to detect a mean difference of 0.33 (SD=0.619) in change from baseline in Schiff sensitivity score after 8 weeks of treatment.

The estimate of SD was obtained from GSKCH study 205794. The sample size is based on carrying out two-tailed two sample t-test at a 5% significance level.

Therefore, to allow for dropouts a sufficient amount of subjects will be screened to randomize approximately 180 subjects to ensure 165 subjects (approximately 55 per arm) complete the study.

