#### 10.2.2 Primary Analysis

The primary efficacy variable is the change from baseline in Schiff sensitivity score at 8 weeks. The primary comparison is between the Experimental formulation and the negative control. As there is only a single primary objective no adjustment for multiple comparisons is required.

The Schiff sensitivity score is derived as the average score of the two test teeth. The change from baseline is derived from the individual teeth first before calculating the average change of the two test teeth.

GlaxoSmithKline Consumer Healthcare Confidential Template Version Effective: 22-Jun-2017 Page **47** of **60** 

The change from baseline in Schiff sensitivity score will be analysed using analysis of covariance (ANCOVA) with treatment as factor and baseline Schiff sensitivity score as a covariate. Note that since the baseline Schiff sensitivity score will be included as a covariate, the baseline Schiff stratification value will not be included in the model.

The assumption of normality and homogeneity of variance in the ANCOVA model will be investigated. In case of violation of these assumptions a suitable transformation or a nonparametric method eg the van Elteren test, adjusting for the maximum baseline Schiff Sensitivity scores will be performed and results will be compared with the ANCOVA results. If the inferences from the two analyses are similar, then both sets of results will be reported and emphasis will be made on the ANCOVA results. If there are differences between the inferences, then the emphasis will be on the non-parametric analysis.

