##### **4.4.1.2 Statistical Hypothesis, Model, and Method of Analysis**

The primary analysis is a comparison of the mean change from baseline Schiff sensitivity score between Test Product and Negative Control at Week 8.

The null hypothesis for the primary endpoint is that the mean change from baseline in Schiff sensitivity score is equal between the 2 products.

$$H_0: \mu_1 = \mu_2$$

The alternative hypothesis is that the mean change from baseline in Schiff sensitivity score is not equal between the 2 products.

$$H_1: \mu_1 \neq \mu_2$$

The change from baseline in Schiff sensitivity score at Week 8 will be analyzed using Analysis of Covariance (ANCOVA) with treatment as factor and mean baseline Schiff sensitivity score as covariate. Note that since the baseline Schiff sensitivity score will be included as a covariate, the baseline Schiff stratification value will not be included in the

---

model. Adjusted means of all treatments and their standard error (SE), P-value and 95% confidence interval (CIs) will be presented on the ITT Population (Table 14.2.1.2). Treatment differences of the treatment comparisons and SE of it will also be provided together with P-values and 95% CIs.

The assumption of normality and homogeneity of variance in the ANCOVA model will be investigated and if violated, data transformations will be investigated. If suitable transformations cannot be found, non-parametric Van Elteren tests will be performed adjusting for the maximum baseline Schiff sensitivity scores and results will be compared with the ANCOVA results. If the inferences from the 2 analyses are similar then both sets of results will be reported and emphasis will be made on the ANCOVA results. In case of discrepancies between p-values of ANCOVA and Van Elteren analysis, inferences will be drawn on the non-parametric analysis.

To visually inspect the treatment effect on Schiff sensitivity scores, a plot across time (Baseline, Week 4 and Week 8) will be displayed with raw means and SE bars. The plot will display a different symbol line for each treatment group (Figure 14.2.1).

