### 4.5 Analysis of Secondary Objectives

#### 4.5.1 Efficacy (Secondary)

##### The change from baseline in tactile threshold at Week 8

The change from baseline in tactile threshold at Week 8 is the secondary efficacy endpoint.

The null hypothesis for the secondary endpoint is that the mean change from baseline in tactile threshold is equal between the 2 products.

$$H_0: \mu_1 = \mu_2$$

The alternative hypothesis is that the mean change from baseline in tactile threshold score is not equal between the 2 products.

$$H_1: \mu_1 \neq \mu_2$$

This secondary efficacy variable analysis will be conducted for the following treatment comparison:

Test Product versus Negative Control at Week 8.

All other treatment comparisons based on the tactile threshold are part of the exploratory objectives.

---

The subjects tactile threshold will be derived as the average score of the 2 test teeth at each visit assessed and the change from baseline will be derived from the individual teeth first before calculating the average change of the 2 test teeth. If tactile threshold for test teeth is reported as “> 80g” at the post baseline assessments, the value will be taken as as 90g in the derivations.

Summary statistics of the observed mean tactile threshold scores and changes from baseline will be presented by treatment at Baseline, Week 4 and Week 8 (Table 14.2.2.1).

The change from baseline in tactile threshold at Week 8 will be calculated as the subject level mean change from baseline (on the 2 test teeth) and analyzed at Week 8 using ANCOVA with treatment and baseline Schiff stratification value as factors and baseline tactile threshold included as a covariate. Adjusted means of all treatments and their SEs, P-value and 95% CIs will be presented. Treatment differences and SE of all pairs of treatments will be provided together with P-values and 95% CIs (Table 14.2.2.2).

To visually inspect the treatment effect on tactile threshold scores, a plot across time, with the raw means together with SE bars will be produced. The plot will display a different symbol line for each treatment group (Figure 14.2.2).

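### The primary Schiff ANCOVA leaves unused the Screening Schiff scores already recorded for the same two test teeth, and SAP 3.2 describes a stratum adjustment that this model does not contain

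*SAP*

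**What the plan says.** SAP 3.2 defines two strata by the maximum baseline Schiff score of the two test teeth (2 or 3) and then states, without exception, "Efficacy variables will be analyzed accounting for strata".

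The models differ in how they treat that factor:

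- **Schiff ANCOVA (primary).** SAP 4.4.1.2 fits the model "with treatment as factor and mean baseline Schiff sensitivity score as covariate". Protocol 10.2.2 says that "the baseline Schiff stratification value will not be included in the model", because baseline Schiff is already a covariate. SAP 4.4.1.2 gives the same reason, and footnote [1] of Table 14.2.1.2 shows the same model. SAP 4.6 carries it to the exploratory Schiff comparisons.
- **Tactile ANCOVA (secondary).** SAP 4.5.1 uses "ANCOVA with treatment and baseline Schiff stratification value as factors and baseline tactile threshold included as a covariate".
- **Van Elteren fallback.** For both endpoints it adjusts for the maximum baseline Schiff score.

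On the earlier reading, footnote 1 of protocol Table 1-1 says "Qualifying Schiff sensitivity and tactile threshold scores will be recorded in the case report form (CRF". Protocol 7.1.2.5 likewise has the qualifying Schiff score transcribed to the CRF. Inclusion criterion 6d requires: "The two selected test teeth must have also qualified at Screening for this criteria". SAP 3.1 defines baseline as the Visit 2 pre-dose value only, and no model in either document uses the Screening scores.

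**The concern.** A test tooth must score 2 or 3 at Baseline, so the only covariate in the primary model is a mean that can take three values: 2, 2.5 or 3. That is a coarse measure of how sensitive a subject is. A second reading of the same teeth, also taken before randomization, could recover some of what a single reading misses. Protocol 1.2.2 asks for two qualifying readings so that consistent responders enter the trial, but the analysis uses only one of them. The primary comparison was sized with no slack, so a small gain in precision would be useful.

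The second matter is that SAP 3.2 and SAP 4.4.1.2 do not agree when read literally. A reader checking the primary model against SAP 3.2 would look for a stratum term and not find one, and the SAP's table of changes from the protocol does not mention it.

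**Working it through.** **1. The plan's own figure.** Protocol 10.1 states "With 55 evaluable subjects per group, the study will have 80% power" for a difference of 0.33 with SD 0.619, using a "two-tailed two sample t-test at a 5% significance level".

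- SE of the difference = 0.619 × √(2/55) = 0.1180.
- 0.33 / 0.1180 = 2.796.
- Normal approximation: power = Φ(2.796 − 1.960) = 79.8%.
- Noncentral t: 79.1% with 108 df; 79.4% with the three-arm error df, 165 − 3 − 1 = 161.

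The stated 80% reproduces.

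**2. What the stratum adds to the covariate already in the model.**

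| Baseline scores of the two teeth | Mean | Maximum | Stratum |
|---|---|---|---|
| 2, 2 | 2 | 2 | 1 |
| 2, 3 | 2.5 | 3 | 2 |
| 3, 3 | 3 | 3 | 2 |

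The mean fixes the stratum. Mean plus stratum can be estimated and is equivalent to a three-level baseline factor, so the stratum contributes one degree of freedom for curvature. A latent-variable simulation was run with both teeth at 2 or 3 at both visits, over 15 scenarios that varied the variance shares and the scale cut-points. It gave the stratum a partial R² of 0.000 to 0.009 beyond the mean. At 0.0093 the SE is multiplied by √(1 − 0.0093) = 0.995 and power is 80.2%, a gain of 0.4 points at the very most. In a second simulation (55 per arm, 3,000 replicates per scenario) adding the stratum changed the SE by between −1.4% and +0.2%, which is about +1.1 to −0.2 power points. The larger gains there arose only when Week 8 was made to depend on the maximum score.

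**3. What the Screening score adds.** The documents give no correlation between Screening Schiff and Week 8 change, so the partial R² beyond mean baseline Schiff is an assumption. With SD replaced by 0.619 × √(1 − R²) and n = 55 per arm (normal approximation):

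| Assumed partial R² | SE multiplier | Power | Change in points |
|---|---|---|---|
| 0 | 1.000 | 79.8% | – |
| 0.01 | 0.995 | 80.2% | +0.4 |
| 0.0128 | 0.994 | 80.3% | +0.5 |
| 0.05 | 0.975 | 81.8% | +2.0 |
| 0.0811 | 0.959 | 83.1% | +3.2 |
| 0.11 | 0.943 | 84.2% | +4.4 |

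The 15 scenarios gave about 0.013 to 0.08. A further check under other assumed correlations gave about 0.01 to 0.11. The second simulation assumed a Screening–Baseline correlation of 0.46 and an SD of change of 0.64 to 0.68. It gave an SE 1.2% to 2.8% smaller where subject sensitivity clearly persists, or about +0.9 to +2.2 points, and an SE 0.3% larger where it does not.

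**4. The downside.** Error df fall from 161 to 160. A covariate with no prognostic value inflates the SE by roughly √(1 + 1/160) = 1.003. That is 0.3%, or about 0.2 power points, and agrees with the simulation.

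**The case against.** The strongest reply is that nothing here is an error. SAP 3.2 is a general statement and does not say that the stratum enters every model as a factor. Protocol 10.2.2 and SAP 4.4.1.2 give the specific rule, agree with each other and state the reason, so no analyst could be unsure which primary model to fit. The fallback test adjusts for the stratum as well. All of this stands, and it reduces the stratum matter to wording.

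On the Screening score, the reply is that baseline is deliberately the value after acclimatization, that Screening scores have the same restricted range (2 or 3 per tooth), and that the gain depends on correlations the documents do not give. It also notes that 0.619 may be an unadjusted SD, in which case the planned ANCOVA may already exceed the stated power. The restricted range and the unknown correlation do limit the gain and make its size uncertain. But the definition of baseline governs the endpoint; it does not bar a second pre-randomization covariate, and acclimatization does not make the earlier reading uninformative.

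A reader might go further and infer any of the following, none of which is supported:

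- **Omitting the stratum biases the primary test or inflates its type I error.** The omission is pre-specified, the covariate determines the stratum, and under randomization an imperfectly shaped covariate does not bias the comparison.
- **Adding the stratum would gain useful precision.** Step 2 of the working shows essentially none.
- **The tactile model should take a Screening tactile covariate too.** No calculation supports this, and with 10 g steps and a 20 g cap a qualifying tooth can read only 10 or 20 g.

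**Conclusion.** The main point holds as a low-cost improvement to the primary analysis. A second pre-randomization Schiff reading on the same two teeth is collected and unused. Using it would probably gain about 0.4 to 3 power points, and somewhat more if the partial R² is nearer 0.11. The cost if it is not prognostic is about 0.3% in SE. The size rests on assumed correlations; the fact that the data are recorded and unused does not.

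The mismatch between SAP 3.2 and the Schiff ANCOVA is real but minor. It calls for consistent wording, has essentially no effect on precision, and leaves the validity of the primary test untouched.

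**What to change.** Before unblinding:

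1. In SAP 4.4.1.2 and 4.6, protocol 10.2.2 and footnote [1] of Table 14.2.1.2, add the mean Screening Schiff score of the two test teeth as a covariate beside mean baseline Schiff. Keep change from the Visit 2 baseline as the endpoint. State how a subject enrolled without a usable Screening score on a test tooth will be handled. If study 205794 recorded Screening Schiff, its partial correlation with Week 8 change would show in advance how much to expect.
2. Make SAP 3.2 agree with the models. Either add the stratum (maximum baseline Schiff 2 or 3) to the Schiff ANCOVA, or reword 3.2 to say that strata enter through mean baseline Schiff in the Schiff ANCOVA and as an explicit factor in the tactile ANCOVA and the van Elteren tests.

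The cost is a few lines of text and one degree of freedom out of about 160, or two if the stratum is also added. With both terms in and neither prognostic, the SE rises by about 0.6%. No new data are needed, and the tactile model stays as it is.
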